4.6 Non-recruited participants

The following anonymised information will be monitored and collected for all potentially eligible participants

- Year of birth
- Date of consultation when approached about the study
- Reason for not participating if willing to give a reason

4.7 Informed consent

Informed consent to participate in the trial will be sought and obtained according to the principles of Good Clinical Practice (GCP). As part of the informed consent process, potential participants will be made aware of all aspects of the study, including the potential risks and their responsibilities. Women will be counselled about additional risks depending on the stage and site of endometriosis in line with standard practice. There is no minimum time that potential participants should be given to decide whether to participate in the trial. Potential participants will be given enough time, and as long as they want, to accept or decline involvement and will be given opportunity to ask questions and to have these answered before giving consent. Consent may be documented using a hard copy consent form during a face to face 'in person' informed consent consultation, or documented by post (following an informed consent in person or telephone discussion), or documented electronically (following an informed consent in person or telephone discussion).

It will be explained that entry into the trial is entirely voluntary and that treatment and care will not be affected by their decision and they can withdraw at any time. In the event of their withdrawal it will be explained that their data collected to date of withdrawal cannot be erased and will be used in the final analyses.

Participants who cannot give informed consent (e.g. due to impaired cognition) will not be eligible for participation. Following informed consent, if a participant loses capacity, the consent given when capable remains legally valid. In such circumstances, a decision needs to be made, in conjunction with the participant and any family or carers, in relation to ongoing participation in the study.

Patients who are not able to read or write (but who have capacity and who can speak English sufficiently to understand the information being provided orally) can agree to take part in the study. In such cases, the study team will provide them with written literature about the study and read and discuss this information with the potential participant. There should also be a discussion about the support networks to which the patient has access to facilitate their participation in the study (e.g. help to complete questionnaires). If the potential participant is fully informed and wishes to take part in the study, they will be asked to sign or make their mark

on the consent form. Their agreement to take part in the study should be witnessed by someone independent from the research team.

Procedures to seek and gain informed consent from eligible potential participants are to be agreed and confirmed by Research Ethics Committees with responsibility for reviewing applications for research. The application for approval is made via the NHS National Research Ethics Service.

Where informed consent is received in person, this should be received by an appropriately trained individual who is listed on the delegation log. Consent forms that are returned by post are checked, signed and dated with the date of receipt by someone who is listed on the delegation log with appropriate delegated responsibilities. The countersignature will only be recorded after discussion has taken place with the participant about the study and any questions have been answered. Only once both patient and person receiving consent signatures are present will informed consent be considered to have been obtained. Participants will be sent a copy of the completed consent form for their own records and a copy will be retained in the investigator site file and TMF.

A copy of the consent form should be forwarded to the trial office for retention in the Trial Master File (TMF).

4.7.1 Obtaining e-Consent

To cater for participant preference and COVID adaptations, participants may opt to consent using an e-consent form via the secure web-based trial management system provided by CHaRT. If this option is preferred, participants will be asked to provide their email address which will be entered into the secure web-based trial management system. Participants will be sent a verification email with a link to verify their email. Once the email address is verified, participants will be automatically emailed the PIL and a link to the participant e-consent form for their unique study number. The e-consent form will be identical to the approved paper version of consent form, with the approved PIL version number and date automatically populated. The participant will be asked to provide their signature online via a signature box using a finger tracing via a touch screen or using a mouse. Completed e-consent forms will be checked, and electronically counter-signed by someone listed on the delegation log with appropriate delegated responsibilities. The countersignature will only be recorded after discussion has taken place with the participant about the study and any questions have been answered. Only once both patient and person receiving consent signatures are present will informed consent be considered to have been obtained. Any e-consent obtained will be verbally confirmed by the site at any future communication. Participants will be sent a copy of the e-consent form for their own records and a copy will be retained in the investigator site file and TMF.

Should participants who are sent the study information choose not to take part in the study their email address will be deleted from the trial management system after 3 months.

The trial management system used to record e-consent has a clear audit trail with tracking of all inserts or updates made. Database interactions logged against a user and date/time and the audit trail can be downloaded and analysed at any time by authorised users.

4.8 Randomisation and allocation

Eligible and consenting participants will be randomised to one of two groups using the proven 24 hour web-based application, hosted by the Centre for Healthcare Randomised Trials (CHaRT) in Aberdeen. The randomisation algorithm will use recruitment site, and age (18-30; 31-40; 41-49 years) as minimisation covariates to allocate to treatment intervention and control groups in a ratio of 1:1. A random element will be incorporated into the randomisation algorithm. A person with delegated authority will access the web-based system. Patient screening

identification initials and recruiting site will be entered into the web-based system which will return the allocation status. At randomisation, an email will be sent to the site research team, including the PI, and the trial office, informing them of the allocation.

4.9 Administration arrangements post recruitment

Following trial entry, the trial office will:

- Notify the GP in writing that a participant has joined the trial.
- Write to the woman confirming her randomisation and what will happen next in the study

The site research team should:

- For those randomised to surgery, add them to the waiting list for surgery, (but can take medical treatment whilst waiting, see section 5.2)
- For those randomised to medical management, arrangements for the medical management should be made (for example commence treatment, provide a prescription or ask the GP to prescribe/administer the treatment)
- File a copy of the consent form in the hospital notes along with information about the trial.
- Enter trial data regarding the participant into the bespoke trial website.
- Maintain trial documentation at site.
- Return a copy of the signed consent form to the Trial Office in Aberdeen.

5. Trial interventions

The current clinical pathway for management of women with pain due to DE involves medical management which may end up with surgery at a later stage.

Women will be offered a choice of hormonal treatments including progestogens, combined contraceptive pill or patch, danazol and GnRH analogues (with add back hormone replacement therapy to reduce menopausal symptoms).

Women with DE randomised to the surgical arm will be offered surgery, after which women who are not trying to conceive may be offered hormonal treatment to reduce the risk of recurrence according to local centre practice/women's choice.

Women in both randomised arms (treated medically or surgically) can be offered analgesics or neuromodulators for additional pain relief. Trial participants randomised to medical management will aim to remain on their allocated medication for 18 months, alterations in medical treatment regime will be allowed but if adequate symptom relief is not achieved then surgery can be offered.

5.1 Medical management

This will involve hormonal treatment for 18 months. The choice of hormonal medication will be at the discretion of the treating clinician in discussion with the participating woman, avoiding any treatment which has either failed or caused unacceptable side effects in the past. The treating clinician will avoid prescribing medication for which the woman has contraindications. Any of the following preparations can be used: the combined contraceptive pill/patch (COCP), progestogen only preparations (oral tablets), depot injections (DMPA), subcutaneous implants or intrauterine systems (LNG-IUS), danazol and gonadotrophin releasing hormone (GnRH) analogues with add back hormone replacement therapy (HRT). Women on hormonal treatment can receive additional neuromodulator drugs, analgesics and other interventions for pain relief. Medical treatment will be prescribed in line with normal and accepted clinical practice, as recommended by NICE guidelines on management of endometriosis⁷ in the UK.

Women may switch between various forms of medical management, depending on their preference and tolerance of various preparations. However, hormonal treatment should continue for 18 months post-randomisation unless:

- A serious adverse reaction to hormonal treatment occurs and in the opinion of the investigator or clinician that it is medically necessary to stop all hormonal treatment.
- A participant wishes to become pregnant.

- The participant declines to start or declines to continue taking hormonal treatment for any reason.

Women in the medical management arm may go on to have surgery, after which they may be offered hormonal contraception to reduce the risk of recurrence according to local centre practice/women's choice.

Regardless of the compliance to medical management women will continue to be followed up within the study.

The medical treatments offered within DIAMOND will not be specifically manufactured or labelled for use within the DIAMOND trial. The trial will use routine stocks prescribed by the clinical team or their GP and dispensed by hospital or local community pharmacy.

5.1.2 Prescription of DIAMOND hormonal treatment

Any hormonal treatment (used as standard of care) may be used. The administration of hormonal treatment will depend on the local policy. The intention would be to initiate the allocated treatment as soon as possible to minimise non-compliance and for the convenience of the participant. The administration of hormonal treatment will usually be in primary care but can be initiated in secondary care or initiated and continued in secondary care. If it is to be administered in primary care, a letter will be sent to the GP specifying the name, dose and duration of hormonal treatment that is being recommended (based on the preference of the participants and their secondary care clinicians) asking the GP to prescribe and initiate treatment. If it is to be initiated in secondary care but ongoing administration is in primary care, a letter will be sent to the GP specifying the name, dose and duration of hormonal treatment that is being recommended (based on the preference of the participants and their secondary care clinicians) asking the GP to continue treatment. If the treatment will be administered purely in secondary care, a letter will be sent to the GP specifying the treatment (for information only).

If the GP does not prescribe/ initiate the hormonal treatment that is recommended this is NOT considered to be a breach of protocol within this pragmatic study and the women will be followed up within the study.

At each follow-up questionnaire, we will ask women to report all treatments that they are receiving. At final follow up, the prescription record for each participant will be requested directly from GP practices or by linking to patient prescribing data (e.g. NHS Digital Data Access Request Service (digital.nhs.uk/data-and-information/data-insights-and-statistics/prescribing-and-medicines-team, www.nhsresearchscotland.org.uk/research-in-scotland/data/health-informatics, in Scotland, or equivalent), to accurately establish medicinal use during the trial. We will seek consent for such linkage at the outset of the study.

5.1.3 Participants' Compliance

Maximising compliance of women to their allocated treatment

We will try to avoid women not commencing the allocated treatment firstly by careful counselling with respect to childbearing intentions. As described in section 5.1.2, women randomised to the medical management arm will have a letter sent to the GP asking them to prescribe and initiate treatment. It is expected that women will receive the medication within 4-6 weeks of randomisation. Women will be asked in their 12 week follow up questionnaire whether or not they have initiated treatment.

5.1.4 Drug accountability

Routine stocks of hormonal treatment will be used. These will be prescribed by the clinical team or their GP and dispensed by hospital or local pharmacy. As the allocated interventions will be taken from normal, non-trial stock the standard NHS labelling for dispensed medicines will apply and study-specific drug accountability records will not be required. If any stock dispensed to women as part of the trial intervention becomes the subject of a medicine recall or

drug alert, this will be handled through routine NHS procedures. Product liability will rest with the holders of the manufacturing authorisations.

5.2 Laparoscopic Surgery (with or without adjuvant medical treatment)

A laparoscopic approach will be used to treat DE but the choice of energy modalities and the need for concomitant hysterectomy and/or oophorectomy will be left to the discretion of the surgeon in consultation with their patient. Rarely a laparotomy may be required to complete the procedure safely

Surgery will involve division of dense adhesions to separate affected pelvic structures, restore normal anatomy and removal of all endometriotic deposits, including deep nodules.

Excision of DE is achieved using laparoscopic instruments such as scissors, hooks and ultrasonic scalpels along with a variety of energy modalities including electricity and ultrasound. If adjuvant medical management is needed, the same medical options used in the medical treatment arm will be utilised including hormones, neuromodulators and pain relief medication.

Women randomised to surgery will be added to the waiting list for surgery soon after randomisation. The research nurse will monitor the surgical lists to identify when surgery has been booked; and thereafter to confirm that surgery has taken place. The participant will be asked to use their usual contraception or barrier contraception until their operation and a pregnancy test will be performed as part of routine care prior to the procedure. If the woman is already taking hormonal treatment to suppress endometriosis symptoms, they will be advised to continue using this until their surgery. For pragmatic reasons, any changes to medical treatment used prior to surgery will be accepted, in line with NICE guidelines⁷.

Excised material will be sent for pathological examination. Women in the surgical arm can use any medical (hormonal) treatment available to those randomised to the medical arm, either for contraception or to prevent recurrence of endometriosis. This will be recorded in each follow up questionnaire.

Any incidental findings that are identified during surgery will be handled as per normal NHS standard of care procedures

5.3 Additional treatment

Women in both randomised arms can be offered analgesics or neuromodulators for additional pain relief. Women in the surgical arm can also be offered hormonal treatment if felt this would be beneficial to the patient's well-being.

6. Outcome Measures

6.1 Primary outcome measure

Primary patient outcome: The primary clinical outcome is the pain domain of the condition-specific Endometriosis Health Profile-30 (EHP-30) measured at 18 months post-randomisation.

Primary economic outcome: incremental cost per quality adjusted life year (QALY) gained from a health service perspective at 18 months and modelled over the reproductive life of women (QALYs derived from participant responses to the EQ-5D-5L).

6.2 Secondary outcome measures

Clinical:

- Surgical complications

Patient reported:

- Condition specific quality of life [EHP 30], four core domains (control, emotional aspects, social support and self-image) measured at 12 weeks, 12 months and 18 months post-randomisation;
- Satisfaction;
- Pain domain of the condition-specific Endometriosis Health Profile-30 (EHP-30) measured at 12 weeks and 12 months post-randomisation;
- Pain (measured on a visual analogue scale) measured at 12 weeks, 12 months and 18 months post-randomisation;
- Further medical treatments (hormones, analgesics, alternative therapies, physiotherapy, TENS etc.);
- Further related surgery;
- Sexual function (EHP-30 + Section C questionnaire);
- Discontinuation of randomised treatment (with reasons for change);
- Serious adverse events and complications;
- Occupational outcome measured by Work Productivity and Activity Impairment questionnaire;
- Indirect costs due to loss productivity;
- Reproductive outcomes (pregnancy, live birth and other obstetric outcomes);
- number of women in the medical treatment arm who go on to have surgery

Economic:

- Indirect costs based on time lost from productive activity measured over the follow-up period (assessed via patient questionnaires).

6.3 Long term outcomes (beyond 18 month horizon)

Data on long-term outcomes (beyond 18 months) including repeat surgery and pregnancy will be obtained by linking with Hospital Episode Statistics (HES) for England, Welsh data for Wales and Information Services Division (ISD) data for Scotland. We will seek consent for such linkage at the outset, but any such linkage will require separate funding.

7. Data Collection and Processing

7.1 Measuring outcomes

Clinical and patient reported outcomes will be assessed at baseline, 12 weeks, 12 months and 18 months post-randomisation using questionnaires.

Table 2 Measurement of outcomes: components and timing

	Baseline	Surgery	12 weeks post-randomisation	12 months post-randomisation	18 months post-randomisation
Baseline CRF ¹	x				
Surgical details CRF ²		x			
EHP-30 + Section C ³	x		x	x	x
EQ-5D-5L ³	x		x	x	x
Satisfaction				x	x
Pain (VAS) ³	x		x	x	x
Initiation of medical management (for those in the medical management arm only)			x		
Further medical treatments ⁴			x	x	x

	Baseline	Surgery	12 weeks post-randomisation	12 months post-randomisation	18 months post-randomisation
Further healthcare resource use			X	X	X
Gynaecological surgery	X			X	X
Discontinuation of randomised treatment (with reasons for change) ⁴			X	X	X
SAEs / complications		X ²	X	X ³	X ³
Occupational outcome measured by Work Productivity and Activity Impairment questionnaire ⁴			X	X	X
Reproductive outcomes ³				X	X
Indirect costs due to loss of productivity ⁴			X	X	X
Case-note review for further treatment ⁵					X

¹ completed by site research team at baseline

² completed by site research team after surgery (for those randomised to surgery and having surgery and those randomised to medical management and having surgery)

³ completed by participant at recruitment and at 12 weeks, 12 months and 18 months post randomisation; combined into a single questionnaire with other participant completed outcomes at same time-points

⁴ completed by participant at 12 weeks, 12 months and 18 months post randomisation; combined into a single questionnaire with other participant completed outcomes at same time-points or CRF completed by site research team

⁵ completed by site research team at 18 months post-randomisation

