7.2 Baseline

Participants will complete the baseline questionnaire (including EHP-30 + Section C and EQ-5D-5L) prior to randomisation.

The site research team will complete the baseline CRF including information on parity; age, ethnicity, current and previous treatments used for endometriosis associated pain.

At baseline, we will also collect contact details of participants (including postal address, email, home and mobile number) and their contact preferences (see section 7.4) along with details of their GP.

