10.1 Sample size

We need primary outcome data on 320 women at 18 months to detect an 8-point difference for the EHP-30 pain domain for 90% power (two-sided alpha 0.05) assuming a standard deviation of 22 points. The 8-point improvement was decided as a clinically important difference for the Pre-Empt trial²⁵ and has now been accepted for use by all new endometriosis trials to allow consistency and comparison of results and future metanalysis. We have assumed an attrition rate of 20% for the primary outcome, which requires us to randomise 400 women in total. The anticipated attrition rate is based on follow up data from BSGE accredited Units which have a dedicated endometriosis nurse and work to a consistent protocol which includes patient completed post-operative questionnaires at 6 and 12 months. As women with DE are all referred for treatment to dedicated endometriosis centres, they are unlikely to be lost to follow-up or choose to seek treatment elsewhere.

Attrition rates will be monitored to detect differential drop-out, which can bias clinical trial results and reduce the power of the trial to detect important differences.

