10.2.3 Project timetable and milestones

The projected timetable start date for the study was 1 January 2021: the study duration will be 52 months. Milestones: prefunding: Research Ethics Committee (REC) and HRA approvals; month 1–6, set-up, authorisations; months 7–28: patient recruitment; months 29–46: patient follow-up to 18 months post randomisation; months 47–52: data analysis, interpretation of results, report writing and dissemination. A Gantt chart is shown below (Figure 3). Due to COVID-19, these milestones have slipped, and we anticipate recruitment commencing in month 10. Figures 2 and 3 will be updated (at the next protocol amendment) once we have established recruitment and the revised timelines are clearer.

Figure 2 Recruitment Projections

[figure not shown]
[figure not shown]

Figure 3: Gantt Chart

11. Statistical analysis

All primary analyses will be based on the intention-to-treat principle. The primary outcome will be analysed using a mixed effects linear model that includes a random effect for centre and participant, with fixed effects for treatment, time, and design covariates, and baseline measure of the primary outcome. Treatment effects will be estimated at each time-point by time-by-treatment interaction. Using EHP-30 scores from each time point will increase precision of estimates. Secondary outcomes will be analysed in a similar way with generalised linear models appropriate for the distribution of the outcome (i.e. logistic regression for binary data). Sensitivities of all treatment effect estimates to missing outcome data will be explored using multiple imputation methods, and pattern mixture modelling to assess the robustness of estimates to that MAR assumption.

A secondary analysis will estimate the direct effect of receiving surgery using Casual Inference Methods. Because receiving surgery in the medical arm will be a time-dependent confounder we will use a marginal structural model (using inverse probability weights) for repeated measures data that will remove the effect of surgery in the medical arm, allowing us

to estimate the treatment effects comparing surgery to medical management without cross-over.

Full details of the statistical analyses will be documented in the Statistical Analysis Plan.

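### The work-productivity scale is scheduled only after randomisation, so the occupational outcome cannot be adjusted for its own baseline and loses precision

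*Protocol*

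**What the plan says.** Protocol section 6.2 lists as a secondary outcome: "Occupational outcome measured by Work Productivity and Activity Impairment questionnaire". Section 2.2 has occupational outcomes among the secondary objectives.

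Table 2 in section 7.1 marks the WPAI row at the three follow-ups and leaves Baseline empty. The footnote attached to the row (footnote 4) agrees with the marks: "completed by participant at 12 weeks, 12 months and 18 months post randomisation". Footnote 3, attached to EHP-30 with Section C, EQ-5D-5L and the pain VAS, adds recruitment to the same three times, and those rows carry a baseline mark.

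The sentence that introduces Table 2 says something different: it lists baseline among the times at which clinical and patient-reported outcomes are assessed, without exception.

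Section 7.2 says: "Participants will complete the baseline questionnaire (including EHP-30 + Section C and EQ-5D-5L) prior to randomisation". It does not name the WPAI there, and it does not name employment among the items on the baseline CRF.

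Section 11 puts the baseline value of the primary outcome into the primary model. Of the rest it says: "Secondary outcomes will be analysed in a similar way with generalised linear models appropriate for the distribution of the outcome".

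**The concern.** Among the scored patient-reported scales for which a pre-treatment value makes sense, the WPAI is the only one not scheduled before randomisation. A woman's own earlier score is usually among the best available predictors of her later score, and adjusting for it is how section 11 gains precision on the primary outcome. For the WPAI that covariate will not exist.

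A schedule that never takes a measurement cannot be repaired by a statistical analysis plan, so this is a matter for the protocol. At stake are the width of the confidence interval on a named secondary outcome, and the ability to describe the arms' work situation before treatment. Section 7.1 also disagrees with itself on when the scale is given.

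**Working it through.** **1. The protocol's own figures.** Section 10.1 sets 320 analysable women as the target and gives this as the basis: "to detect an 8-point difference for the EHP-30 pain domain for 90% power (two-sided alpha 0.05) assuming a standard deviation of 22 points". Section 4.8: "allocate to treatment intervention and control groups in a ratio of 1:1". The normal formula gives n per arm = 2 × (1.960 + 1.282)² × (22/8)² ≈ 159, or 318 in total. The t-based version gives 160 per arm, or 320. Power at 160 per arm is 90.2%. For dropout, 320/0.80 = 400, matching "We have assumed an attrition rate of 20% for the primary outcome, which requires us to randomise 400 women in total". These figures reproduce and are not in dispute; they set the scale for what follows.

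**2. Effect of lacking the baseline.** Let r be the correlation between baseline and follow-up WPAI. The protocol gives no value, so 0.3 to 0.7 is an assumed range. At one follow-up time, which fits section 11 because it estimates the effect at each time-point:

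- variance with adjustment relative to none = 1 − r²
- variance inflation from having no baseline = 1/(1 − r²)
- confidence-interval width with adjustment relative to none = √(1 − r²)
- difference detectable at 90% power, in SD units, with 160 per arm = 3.242 × √(2/160) × √(1 − r²) = 0.362 × √(1 − r²)

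| Assumed r | 1 − r² | Inflation without baseline | Relative CI width | Detectable difference (SD) | Power at a true 0.30 SD | Adjusted women giving the same precision as 320 unadjusted |
|---|---|---|---|---|---|---|
| no adjustment | 1.00 | – | 1.00 | 0.362 | 76.5% | – |
| 0.3 | 0.91 | 1.10 | 0.95 | 0.346 | 80.3% | 291 |
| 0.5 | 0.75 | 1.33 | 0.87 | 0.314 | 87.3% | 240 |
| 0.7 | 0.51 | 1.96 | 0.71 | 0.259 | 96.4% | 163 |

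The 0.30 SD effect is illustrative. The table takes all 320 women as contributing a score. If only a fraction do, the detectable differences grow but the ratios do not change.

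**3. If a baseline already collected is used instead.** Suppose baseline EHP-30 pain, EQ-5D-5L or VAS correlates q with follow-up WPAI and adds nothing once baseline WPAI is known. The inflation then falls to (1 − q²)/(1 − r²). With q = 0.3 and r = 0.5 (both assumed) it is 0.91/0.75 = 1.21 rather than 1.33.

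**4. If only some women have the new baseline.** With a share p of analysed women having it and an indicator for the others, the average residual variance is about p(1 − r²) + (1 − p) = 1 − p·r². With p = 0.5 and r = 0.5 (both assumed) this is 1 − 0.125 = 0.875, so half of the 25% reduction is obtained.

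**5. How many women a change could reach.** Section 10.2.3 starts the study on 1 January 2021 with recruitment in months 7 to 28, which is 22 months, and expects the start to slip to month 10. Twenty-two months from month 10 ends in month 31. Version 7 is dated 9 May 2023, which is month 29. On that timetable little recruitment remained. The protocol does not give the actual recruitment status.

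**The case against.** Four points on the other side have weight.

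First, a reader might infer that the analysis stated for secondary outcomes is impossible for the WPAI. Section 11 does not support that. It names a baseline term for the primary outcome only, and its wording for the others ("Secondary outcomes will be analysed in a similar way with generalised linear models appropriate for the distribution of the outcome") cannot promise an own-baseline term for each, since satisfaction, further surgery and pregnancy have none. No commitment is broken.

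Second, a reader might infer that lost-productivity costs also need a baseline. They do not. Section 6.2 defines them over follow-up, and section 12 states no baseline adjustment for them and presents them only alongside a health-service analysis.

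Third, it is tempting to say that defining the work-time population by baseline employment would protect the comparison. The protocol does not describe how the scale is scored. If work-time scores exist only for women in work, a woman employed at baseline who later stops still has no follow-up score. The post-randomisation loss remains.

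Fourth, the baseline questionnaire may already hold work items. The list in section 7.2 is open, and it omits the pain VAS, which Table 2 does mark at baseline. This is possible, but the WPAI row and its footnote agree with each other. If work items are in fact collected, the row and footnote are wrong and still need correcting.

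It also stands that chance imbalance is already reflected in the confidence interval, and that the primary outcome, sample size, EHP-30 and EQ-5D-5L analyses are untouched.

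**Conclusion.** The point holds as a loss of precision on one named secondary outcome, together with an inconsistency inside section 7.1. It is not a bias, and it does not break a stated analysis.

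Against no adjustment, variance is inflated by 1.10 to 1.96 for an assumed r of 0.3 to 0.7. At r = 0.3, adjustment would narrow the interval by only about 5%; at r = 0.7, by about 29%. The inflation is smaller if another baseline scale serves as covariate, and the recoverable part shrinks in proportion to the share of women already randomised. The conclusion rests on reading Table 2 and its footnote as the schedule in force. It merits a correction because the remedy is cheap, but its weight is modest.

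**What to change.** - **Women still to be randomised:** add the WPAI, with employment status, to the pre-randomisation questionnaire. Mark Baseline in the WPAI row of Table 2 and name the scale in section 7.2. Amend footnote 4 for this row. That footnote also governs rows that need no baseline, so moving the WPAI row to footnote 3 is the simplest way.
- **Section 7.1:** bring the introductory sentence and Table 2 into agreement on which outcomes are assessed at baseline.
- **Analysis:** include baseline WPAI as a covariate in the WPAI model. For women already randomised, use a missing-indicator or mean imputation for this covariate, which is acceptable because whether it was collected is settled before allocation. Adjust as well for a baseline measure in hand, such as EHP-30 pain or EQ-5D-5L.
- **Reporting:** give employment status at each follow-up by arm for all women, so that any loss of work-time scores after randomisation can be seen.
- **No change** is needed to the indirect-cost row.

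The cost is an amendment and a few extra baseline questions. The gain is confined to women not yet randomised. If recruitment has closed, what remains is adjustment for a baseline already collected, the employment report and the correction to section 7.1.
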